If the sensory threshold, highest acceptable amplitude and/or motor threshold are not observed, this will be documented. The Investigator or delegated personnel should try repeating the motor and sensory assessment with the foot in a different position. If the motor and/or sensory response is still not observed, the Investigator or delegated personnel should set neurostimulator amplitude to 3 mA unless an alternative amplitude level is recommended by the Sponsor.

The investigator or delegated personnel may initiate the therapy at this time. If the subject would prefer a different time to start therapy, the subject will be instructed to initiate their therapy schedule for their therapy session at a time convenient for them within approximately 24 hours after their visit.

Programming and device data (e.g., Usage Report, Session Report) will be collected in accordance with device instructions prior to the subject leaving the visit and transferred to Medtronic using the application on the handset and/or collected on the programming worksheet provided.

The following guidance will be provided to study subjects:

- You may return to normal activity levels
- If the subject decides to turn therapy on after the visit, turn on stimulation for the next therapy session following the instructions:
 - It is recommended that the subject will receive 30 minutes of stimulation (Therapy Schedule #1) every other day. The therapy schedule may be adjusted based on symptom control and/or patient preference.
- If the subject is comfortable with the stimulation sensation, they can resume normal activities during their therapy sessions.
- Subjects may feel sensation or notice a motor response during their therapy sessions.
- Any changes to the stimulation should be made within the first five minutes of each therapy session.
- It is recommended that the device is recharged weekly.

Any adverse events and/or device deficiencies will be collected.

3-Month Follow-up Visit:

The 3-day urinary voiding diary should be started approximately one week prior to the study visit. If the diary is not able to be completed prior to the visit, it will be completed immediately following the study visit. The Overactive Bladder Quality of Life Questionnaire (OAB-q), [REDACTED]

[REDACTED], [REDACTED] Urgency Perception Scale (UPS) [REDACTED] will be collected.

The subject will have an impedance check and sensory/motor threshold testing done with their foot in the same relaxed position as the time of implant. The subject's sensory and motor threshold will be identified using 20 hertz, 200 microseconds pulse width stimulation and titrating up amplitude until the sensory threshold, highest acceptable amplitude and motor threshold are confirmed. The neurostimulator amplitude should be set to the highest acceptable amplitude. If highest acceptable amplitude is unable to be found, it is recommended to set the amplitude to two times the motor or sensory threshold, whichever is lower. The comfort of the programmed amplitude will be verified while the subject is in expected positions and adjusted for comfort, if needed.

If the sensory threshold, highest acceptable amplitude and/or motor threshold are not observed, this will be documented. The Investigator or delegated personnel should try repeating the motor and sensory assessment with the foot in a different position. If the motor and/or sensory response is still not observed, the Investigator or delegated personnel should set neurostimulator amplitude to 3 mA unless an alternative amplitude level is recommended by the Sponsor.

The investigator or delegated personnel may initiate the therapy at this time. If the subject would prefer a different time to start therapy, the subject will be instructed to initiate their therapy schedule for their therapy session at a time convenient for them within approximately 24 hours after their visit.

Programming and device data (e.g., Session Report, Usage Report) will be collected in accordance with device instructions prior to the subject leaving the visit and transferred to Medtronic using the application on the handset and/or collected on the programming worksheet provided.

The following guidance will be provided to study subjects:

- If the subject decides to turn therapy on after the visit, turn on stimulation for the next therapy session following the instructions:
 - It is recommended that the subject will receive 30 minutes of stimulation (Therapy Schedule #1) every other day. The therapy schedule may be adjusted based on symptom control and/or patient preference.
- If the subject is comfortable with the stimulation sensation, they can resume normal activities during their therapy sessions.
- Subjects may feel sensation or notice a motor response during their therapy sessions.
- Any changes to the stimulation should be made within the first five minutes of each therapy session.
- It is recommended that the device is recharged weekly.

Any adverse events and/or device deficiencies will be collected.

6-Month Follow-up Visit:

The 3-day urinary voiding diary should be started approximately one week prior to the study visit. If the diary is not able to be completed prior to the visit, it will be completed immediately following the study visit. The Overactive Bladder Quality of Life Questionnaire (OAB-q), [REDACTED]

Scale (UPS) [REDACTED] will be collected.

Urgency Perception

The subject will have an impedance check and sensory/motor threshold testing done with their foot in the same relaxed position as the time of implant. The subject's sensory and motor threshold will be identified using 20 hertz, 200 microseconds pulse width stimulation and titrating up amplitude until the sensory threshold, highest acceptable amplitude and motor threshold are confirmed. The neurostimulator amplitude should be set to the highest acceptable amplitude. If highest acceptable amplitude is unable to be found, it is recommended to set the amplitude to two times the motor or sensory threshold, whichever is lower. The comfort of the programmed amplitude will be verified while the subject is in expected positions and adjusted for comfort, if needed.

If the sensory threshold, highest acceptable amplitude and/or motor threshold are not observed, this will be documented. The Investigator or delegated personnel should try repeating the motor and sensory assessment with the foot in a different position. If the motor and/or sensory response is still not observed, the Investigator or delegated personnel should set neurostimulator amplitude to 3 mA unless an alternative amplitude level is recommended by the Sponsor.

Following the 6-month follow-up visit, the programmed therapy session may include any of the following based on symptom control and/or patient preference: remaining on 30 minutes stimulation every other day (Therapy Schedule #1), stimulation for 30 minutes every day (Therapy Schedule #2), stimulation for 30 minutes every third day (Therapy Schedule #3), stimulation for 60 minutes every other day (Therapy Schedule #4), stimulation for 30 minutes once per week (Therapy Schedule #5), stimulation for 60 minutes every day (Therapy Schedule #6), stimulation for 4 hours every day (Therapy Schedule #7), stimulation for 8 hours every day (Therapy Schedule #8) or custom stimulation (Therapy Schedule #9). The investigator or delegated personnel may initiate the therapy at this time. If the subject would prefer a different time to start therapy, the subject will be instructed to initiate their therapy schedule for their therapy session at a time convenient for them within approximately 24 hours after their visit.

Programming and device data (e.g., Usage Report, Session Report) will be collected in accordance with device instructions prior to the subject leaving the visit and transferred to Medtronic using the application on the handset and/or collected on the programming worksheet provided.

The following guidance will be provided to study subjects:

- If the subject decides to turn therapy on after the visit, turn on stimulation for the next therapy session within 24 hours after their visit.

- If the subject is comfortable with the stimulation sensation, they can resume normal activities during their therapy sessions.
- Subjects may feel sensation or notice a motor response during their therapy sessions.
- Any changes to the stimulation should be made within the first five minutes of each therapy session.
- It is recommended for the device to be recharged weekly. More frequent recharging may be required based on the selected program. A different program may be considered if recharge durations are too long.

Any adverse events and/or device deficiencies will be collected.

12-Month and 24-Month Follow-up Visits:

The 3-day urinary voiding diary should be started approximately one week prior to the study visit. If the diary is not able to be completed prior to the visit, it will be completed immediately following the study visit. The Overactive Bladder Quality of Life Questionnaire (OAB-q), [REDACTED]

Urgency Perception Scale (UPS) [REDACTED] will be collected.

The subject will have an impedance check and sensory/motor threshold testing done with their foot in the same relaxed position as the time of implant. The subject's sensory and motor threshold will be identified using 20 hertz, 200 microseconds pulse width stimulation and titrating up amplitude until the sensory threshold, highest acceptable amplitude and motor threshold are confirmed. The neurostimulator amplitude should be set to the highest acceptable amplitude. If highest acceptable amplitude is unable to be found, it is recommended to set the amplitude to two times the motor or sensory threshold, whichever is lower. The comfort of the programmed amplitude will be verified while the subject is in expected positions and adjusted for comfort, if needed.

If the sensory threshold, highest acceptable amplitude and/or motor threshold are not observed, this will be documented. The Investigator or delegated personnel should try repeating the motor and sensory assessment with the foot in a different position. If the motor and/or sensory response is still not observed, the Investigator or delegated personnel should set neurostimulator amplitude to 3 mA unless an alternative amplitude level is recommended by the Sponsor.

During annual visits, the programmed therapy session may include any of the following: 30 minutes stimulation every other day (Therapy Schedule #1), stimulation for 30 minutes every day (Therapy Schedule #2), stimulation for 30 minutes every third day (Therapy Schedule #3), stimulation for 60 minutes every other day (Therapy Schedule #4), stimulation for 30 minutes once per week (Therapy Schedule #5), stimulation for 60 minutes every day (Therapy Schedule #6), stimulation for 4 hours every day (Therapy Schedule #7), stimulation for 8 hours every day (Therapy Schedule #8) or custom stimulation (Therapy Schedule #9). The investigator or delegated personnel may initiate the therapy at this time. If the subject would prefer a different time to start therapy, the subject will be instructed to

initiate their therapy schedule for their therapy session at a time convenient for them within approximately 24 hours after their visit.

Programming and device data (e.g., Usage Report, Session Report) will be collected in accordance with device instructions prior to the subject leaving the visit and transferred to Medtronic using the application on the handset and/or collected on the programming worksheet provided.

At the completion of the 24-month follow-up visit (along with the final voiding diary), the subject will be exited from the study. All programming completed at the visit will be up to the investigator's discretion. Any adverse events and/or device deficiencies will be collected.

The TNM neurostimulator may remain implanted following study exit; the decision whether to explant will be per physician and patient discretion. [REDACTED]

[REDACTED] Subjects should be given instructions to contact the study doctor or research coordinator if any component of the TNM system is lost, damaged or malfunctions following completion in the study.

Follow-up Visit Data Collection:

Table 4 outlines requirements for each follow-up visit, including unscheduled visits. Based on the visit requirements, the following data points may be collected.

For logistical and public safety issues (e.g., global pandemic), remote collection of follow-up data will be allowed along with remote device access/programming with enabling software (as applicable). If available during the study, Medtronic may use remote support to access programming data.

In addition to collection of adverse events, device deficiencies, OAB medications, protocol deviations and study exit data, data points are described, but not limited to, the following sections.

- Post-operative care (e.g., wound healing, compression use, activity level assessment questions, etc.)
- Voiding diary
- Questionnaires: OAB-q, [REDACTED] UPS, [REDACTED]
- Motor and sensory threshold data
- Programming/device/recharge data

Periodic Progress Check-in Calls:

Following the device implant, it is recommended that site personnel contact study subjects within approximately 48 hours after each study visit and approximately one week prior to each upcoming visit. In addition to these calls, monthly check-in calls will be recommended to start following the 3-month follow-up visit. The intent of the call will be to verify the handset "stimulation on" slide button is on,

provide recharge reminders for the handset, communicator and wireless recharger and provide any reminders for upcoming visits (e.g., diary completion).

Any adverse events and/or device deficiencies will be collected.

Unscheduled Visits

An unscheduled visit may be needed for any device-related reason. During the visit, any OAB medication changes, adverse events and/or device deficiencies will be collected. A 3-day urinary voiding diary may be completed.

If any programming changes are made during the visit, the subject will have an impedance check and sensory/motor threshold testing done with their foot in the same relaxed position as the time of implant. The subject's sensory and motor threshold will be identified using 20 hertz, 200 microseconds pulse width stimulation and titrating up amplitude until the sensory threshold, highest acceptable amplitude and motor threshold are confirmed. The neurostimulator amplitude should be set to the highest acceptable amplitude. If highest acceptable amplitude is unable to be found, it is recommended to set the amplitude to two times the motor or sensory threshold, whichever is lower. The comfort of the programmed amplitude will be verified while the subject is in expected positions and adjusted for comfort, if needed.

If the sensory threshold, highest acceptable amplitude and/or motor threshold are not observed, this will be documented. The Investigator (or delegated personnel) should try repeating the motor and sensory assessment with the foot in a different position. If the motor and/or sensory response is still not observed, the Investigator (or delegated personnel) should set neurostimulator amplitude to 3 mA unless an alternative amplitude level is recommended by the Sponsor.

The subject should have the appropriate program set based on study requirements.

Programming and device data (e.g., Usage Report, Session Report) will be collected in accordance with device instructions prior to the subject leaving the visit and transferred to Medtronic using the application on the handset and/or collected on the programming worksheet provided.

System Modification:

If the device needs to be explanted or replaced at any time after the implant procedure, a System modification procedure will be scheduled. System modifications will include device replacements and explants. Subjects will be encouraged to complete a voiding diary prior to any system modification procedure. Prior to neurostimulator removal and/or after a new neurostimulator is placed, an ultrasound image to assess measurements related to the tibial nerve may be completed.

During the visit, any relevant medication changes, procedural data, adverse events and/or device deficiencies will be collected. Sensory and/or motor thresholds should be assessed (when possible) prior to the implant procedure. Device programming (e.g., Usage Report, Session Report) will be collected in

accordance with device instructions and documented on the programming worksheet prior to the explant (when possible) and at the time of any new implant procedures. The therapy schedule will be set based on the timeframe in the study when the system modification was completed, and the therapy session may be initiated during the visit or within 24 hours.

Post-operative instructions should be followed for any replacement neurostimulators. Following a system modification, the subject should complete a 7-day post procedure visit. In addition, the subject will receive a 1-month post-procedure call in order to assess compression, wound healing, activity levels, etc. The subject will then continue their follow-up schedule based on the initial device implant date.

Post-operative instructions should be followed for any device explant which is not associated with a device replacement procedure. The subject will receive a 1-month phone call in order to confirm resolution of any ongoing adverse events. It is recommended to follow the subject until all ongoing related AEs are resolved or unresolved with no further actions planned.

No replacement neurostimulators will be provided after participation in the study has ended.

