All subjects must wear a compression sock for at least 72 hours and possibly up to two weeks after device implant. The duration of compression will be determined by the Investigator using the study-specific recommendations which are based on pocket size, motor and/or sensory thresholds and pertinent medical history of the subject.

The subject will be provided post-implant care instructions within the informed consent form and Post-Implant Subject Instructions (outlined below) to explain how to manage their implanted device. Post-implant care and activity guidelines identified below should be reviewed with subjects prior to the end of the visit.

Post-implant Care

To aid healing and minimize the chance for device movement, provide the following guidance to subjects.

Following the implant procedure:

- Subjects should be instructed to consult study physician if they notice any unusual symptoms or signs (for example, swelling, or redness at the incision site).
- Cold packs may be used after implant for comfort. A barrier (for example a towel) may be placed between the cold pack and the compression sock to keep the sock dry.

- Subjects may experience soreness or pain when walking or flexing the ankle while healing from the implant procedure.
- Subjects must be instructed to wash hands before handling the bandage or compression sock and avoid touching the implant site.

For the first 3 days:

- The implant site must be kept covered with the bandage applied during procedure for 72 hours or based on the physician's instructions.
- The implant site must be kept dry for 72 hours. Shower bags can be used to help keep the site dry.
- A compression sock must be used for at least 72 hours, or longer if the physician advises the subject to. This will aid in healing around the device. If the subject is advised to use a compression sock for longer than 72 hours, a shower bag should be used while showering to keep the site dry for the duration that the subject wears the compression sock.
- If the compression sock gets wet, replace with a dry compression sock.

For the first 2 weeks:

- Avoid scrubbing the incision site for 2 weeks or until the wound is closed.

For the first 4 weeks:

- Avoid soaking the incision site (e.g., taking a bath, swimming, using a hot tub) for 4 weeks.

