- Avoid strenuous, long duration and high impact activities; for example: aerobics, cycling, running, swimming, long walks, recreational sports, and gym exercises involving the foot, leg, or ankle (elliptical, leg press, etc.) during the 4 weeks while the device is encapsulating. Subjects should limit physical activities to short duration (30 minutes) and low intensity activities during this time.
- Wear flat shoes (no heels) for 4 weeks. Avoid wearing shoes or boots that rub or are tight around the implanted device.

In addition to post-implant care, the following guidance will be provided to study subjects:

- Subjects should turn on stimulation for the next therapy session following the instructions (Therapy Schedule #1; stimulation for 30 minutes every other day) during the visit or at a time convenient for them within 24 hours of the visit.
- During recovery it is recommended that subjects receive therapy with their leg in a relaxed position, or in the position where sensory testing was assessed during the post implant testing.
- Subjects may feel sensation or notice a motor response during their therapy sessions.
- Any changes to the stimulation should be made within the first five minutes of each therapy session.

- Subjects will be reminded they are prohibited from taking overactive bladder pharmacotherapy until after the 12-month follow-up visit.

Any adverse events and/or device deficiencies will be collected.

The following information should be collected at the implant visit:

- Procedure details
- System information (e.g., model number, serial/lot number, etc.)
- Motor and sensory threshold data
- Programming and device data
- Ultrasound images (if applicable)
- Post-operative care (e.g., infection control, compression sock duration, etc.)
- Any adverse events and/or device deficiencies
- Any study deviations

7-Day Post-Procedure Follow-up Visit:

The compression sock will be removed if it was still recommended for the subject.

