10.3 Scheduled Follow-up Visit Windows

Should a subject miss a visit or the visit falls outside the pre-specified window, a study deviation must be reported, and the original follow-up schedule maintained for subsequent visits.

Data analyses include follow-up visits, regardless of whether the visit occurs within the window. Therefore, a late visit is preferred over a missed visit but must be accompanied with a reported study deviation. Follow-up visit windows are listed in Table 5 and are based on days post-implant.

Table 5: Study Follow-up Visit Windows

Study Follow-up Visit	Window (Calculated calendar days post-implant; implant is Day 0)		
	Window Start (days post-implant)	Target (days post-implant)	Window End (days post-implant)
7-Day Post-Procedure Follow-up Visit	4 days	7 days	10 days
1-Month Follow-up Visit	20 days	30 days	40 days
2-Month Follow-up Visit	46 days	60 days	74 days
3-Month Follow-up Visit	76 days	90 days	104 days
6-Month Follow-up Visit	150 days	180 days	210 days
12-Month Follow-up Visit	330 days	360 days	390 days
24-Month Follow-up Visit	660 days	720 days	780 days

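### The 1-month visit script lifts the activity limit without condition, yet the visit may fall up to 8 days before the 4-week limit ends

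*Protocol*

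**What the plan says.** Protocol section 10.1, Post-implant Care, sets limits for the first 4 weeks. Subjects are to avoid strenuous, prolonged or high-impact activity "during the 4 weeks while the device is encapsulating", and "Subjects should limit physical activities to short duration (30 minutes) and low intensity activities during this time". The section gives the reason: "To aid healing and minimize the chance for device movement, provide the following guidance to subjects".

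Later in 10.1, the list of guidance to be given to subjects at the 1-month and 2-month visits opens with "You may return to normal activity levels". No day count, wound check or investigator judgement is attached. The one nearby condition, comfort with the stimulation sensation, governs activity during therapy sessions only.

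Section 10.3 states: "Follow-up visit windows are listed in Table 5 and are based on days post-implant". Implant is day 0. Table 5 gives the 1-month visit a window of days 20 to 40 (target 30) and the 2-month visit a window of days 46 to 74 (target 60).

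For replacements, 10.1 (System Modification) says "Post-operative instructions should be followed for any replacement neurostimulators". It adds a 7-day visit, and "the subject will receive a 1-month post-procedure call in order to assess compression, wound healing, activity levels, etc". It then says "The subject will then continue their follow-up schedule based on the initial device implant date".

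**The concern.** Two instructions to the same subject can contradict each other while the site complies with the plan. The first sets a 4-week limit with a stated safety purpose. The second is later, unconditional and addressed directly to the subject, so it reads naturally as ending the first. The window lets the second arrive before the first has run out. An early visit inside the window is not a deviation, so deviation reporting would not flag the early release.

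What is at stake is a safeguard that the sponsor itself set against device movement. The plan takes that hazard seriously: section 11.1 lists migration as a risk, section 12.1 says when movement is to be reported as an adverse event, and section 11.3 pauses enrollment and implantation after 7 subjects have migration leading to explant. The documents contain no data linking activity on days 20 to 27 to migration, so the point concerns the instruction and not any count, pause decision or endpoint.

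**Working it through.** There is no plan figure to reproduce; the check is calendar arithmetic.

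**Inputs**
- Activity limit: 4 weeks from implant (10.1, Post-implant Care) = 4 × 7 = 28 days.
- 1-month visit: days 20 to 40, target 30 (10.3, Table 5).
- 2-month visit: days 46 to 74, target 60 (10.3, Table 5).
- Day 0 = implant (10.3, Table 5).

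**First implant, 1-month visit.** A visit on day V conflicts if V < 28.
- Permitted days: 40 − 20 + 1 = 21.
- Conflicting days: 20 to 27, which is 27 − 20 + 1 = 8.
- Share of permitted days: 8/21 = 38%.
- Earliest visit: 28 − 20 = 8 days early. Latest conflicting visit: 28 − 27 = 1 day early.
- Days without conflict: 28 to 40 = 13.
- At target: 30 − 28 = 2 days after the limit ends, so no conflict.

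**First implant, 2-month visit.** The window has 74 − 46 + 1 = 29 days. None is before day 28, so 0 of 29 conflict.

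**Replacement.** Let R be the day of the new implant, counted from the original implant. The limit restarts at R, but visits remain on the original clock. A visit on day V conflicts if 0 < V − R < 28.
- 1-month visit at target, V = 30: R from 3 to 29.
- 2-month visit at target, V = 60: R from 33 to 59.

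**After the fix.** If the release waits for 28 days from the latest implant, the maximum early release falls from 8 days to 0 for a first implant, and the replacement conflict also disappears.

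**The case against.** The strongest reply is that a sensible site would read the two instructions together. The release is permissive, the limit is dated and explained, and subjects receive the limit at the implant visit and in written instructions. The visit is called 1-month and targeted at day 30, so the intended order is plain: the limit ends at day 28 and release follows. Section 10.1 also lists activity-level questions among the follow-up data that may be collected, so the line need not be delivered mechanically. This shows what was intended and why the matter is minor. It does not remove the conflict: compliance is defined by the window rather than the target, and nothing in the plan makes the release wait for week 4.

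A second reply is that 8 of 21 says nothing about how many visits fall early. That is correct. It counts permitted days, and the documents give no distribution of visit timing.

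A third concerns replacements. The protocol restates the post-operative instructions for them, adds a 7-day visit and a 1-month call on the new clock, and only then says the regular schedule continues. One could read this as resuming the schedule after the call. But both the synopsis and 10.1 tie later visits to the original implant date and neither suspends a scheduled visit, so overlap is a fair reading. The extra contacts soften the problem without changing what the scheduled visit tells the subject. How often early replacements occur is not stated.

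Finally, the consent materials and device labeling are supplied separately (sections 18.1 and 18.3) and may already carry the condition. That cannot be checked here, and it would not correct the protocol script.

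**Conclusion.** The concern holds. For a first implant, an in-window 1-month visit on days 20 to 27 releases the subject from the activity limit 1 to 8 days early; the other 13 permitted days, and the whole 2-month window, are consistent. After a replacement, a 1-month or 2-month visit less than 28 days after the new implant gives the same early release.

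This rests on reading 4 weeks as 28 days from implant, with day 28 the first unrestricted day, and on the site following the script as worded. For replacements it also rests on scheduled visits going ahead on the original clock. The conflict covers activity only; the 4-week advice on soaking and footwear is not touched by the release line. The number of subjects affected and any effect on device movement cannot be derived from the documents. The issue is minor but should be corrected, since it is a direct safety instruction to people with a new implant.

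**What to change.** In the 1-month and 2-month guidance in section 10.1, keep "You may return to normal activity levels" and add this condition: once 4 weeks have passed since your most recent device implant or replacement. Use the same wording in the subject instructions. The 4-week limit, the Table 5 windows and the replacement schedule can stay as they are. Recording the date of release is optional.

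The cost is one clause in the protocol and the matching line in the subject materials, with no new visit, procedure or data field. Section 16.6 requires IRB approval, and FDA approval as applicable, before a revision is implemented, so the change is best carried in the next planned revision.
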